12.6 Analysis of Safety Data

The primary safety analyses will be based on the as-treated population, defined as subjects who are randomized and receive at least one dose of study agent. Safety endpoints will include ocular adverse events, ophthalmic exam findings, and use of rescue treatments. The occurrence of ocular adverse events will be recorded from the time of randomization through the last study visit. AEs will be categorized by System Organ Class (SOC) Preferred Term (PT) using the Medical Dictionary for Regulatory Activities (MedDRA) and by severity using the Common Terminology Criteria for Adverse Events (CTCAE) dictionary.

In general, all AE tables will be presented by treatment group, causality and severity. Events in the right and left eyes will be considered as separate events. The following will be summarized and presented overall and by treatment group:

- The number and percentage of subjects experiencing an SAE.
- The number and percentage of subjects experiencing an SAE by preferred term and by severity of event.
- The number and percentage of subjects experiencing an SAE by preferred term and by relationship to study drug.

- The number and percentage of subjects experiencing an AE.
- The number and percentage of subjects experiencing an AE by preferred term and by severity of event.
- The number and percentage of subjects experiencing an AE by preferred term and by relationship to study drug.
- The number and percentage of AEs that cause a subject to discontinue study drug.
- The number and percentage of AEs leading to death.

13 Data Management

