- Poor refractive outcome (worse than 20/40 at 3 months or beyond)
- Pain or severe irritation at 3 months or beyond
- Corneal erosion
- Corneal haze
- Need for touch up surgery

There is a theoretical risk of infection with amniotic fluid drops. A patient could have an immune reaction to the study drops.

6.1.3 Treatment or Action Taken:

For each adverse event, the site investigator will record whether an intervention was required:

- Medical or surgical procedure
- Concomitant medication: started, changed, or discontinued
- Other, specify
- No action taken

6.1.4 Outcome of Event:

Finally, the site investigator will record the clinical outcome of each adverse event as follows:

- Death
- Recovered and the patient returned to baseline status
- Recovered with permanent sequelae
- Symptoms persist

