Based on numerous power estimates (the above and others), a sample size of 56 patients completing the trial, yields acceptable power to find a significant treatment difference, if the true treatment difference is at least 0.5 days for the time to complete re-epithelialization outcome. In order to collect additional safety data and allow for a small number of patients being lost to follow-up, the study will enroll a total of 63 participants.

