7. ANALYSIS POPULATIONS

The following analysis populations are planned for the pAF after PRK trial:

- **Eligible Population:** The Eligible Population includes all subjects who are screened for eligibility into the trial, and meet the trial inclusion and exclusion criteria. This population, which will be equivalent to all subjects who received a study identification number, will be used for reporting of study flow per CONSORT guidelines.
- **Intention to Treat Population (ITT):** The Intention-to-Treat Population includes all subjects who provide informed consent and who are randomized into the trial, regardless of whether treatment was initiated or adherence to the protocol.
- **Modified Intention to Treat Population (mITT):** The Modified Intention-to-Treat Population includes all subjects in the ITT population

who receive PRK, and who have analyzable primary outcome data for at least one PRK-treated eye.

- **Safety Population:** The Safety Population includes all patients who received PRK, and who receive treatment with at least one drop of study agent during the post-treatment follow-up.
- **Per-Protocol Efficacy:** The PP-Efficacy population includes patients in the ITT population who are verified to meet all study inclusion and exclusion criteria, and who receive the full assignment treatment, as specified in the protocol, throughout the duration of follow-up.

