8.2 Methods for Withdrawals, Missing Data, and Outliers

Per the intention-to-treat principle, any subjects who withdraw from the study will have all available data used in the analysis, per outcome-specific analysis strategies specified elsewhere in this SAP. In the unexpected event that a substantial number of subjects are lost to follow-up or otherwise withdrawn, baseline characteristics and available information on components of efficacy outcomes will be reviewed and compared to subjects not withdrawn, to assess empirically if these subjects differ from those remaining in the study for the scheduled treatment and follow-up time.

Outliers will be reviewed for validity. Outliers that are valid (e.g., reports of extremely poor visual acuity during follow-up) will be included in all primary reports from this trial.

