11. SAFETY ANALYSES

11.1 Ocular Adverse Events

The primary safety analyses will be based on the as-treated population, defined as subjects who are randomized and receive at least one dose of study agent. Safety endpoints will include ocular adverse events, ophthalmic exam findings, and use of rescue treatments. The occurrence of ocular adverse events will be recorded from the time of randomization through the last study visit. AEs will be categorized by System Organ Class and Preferred Term using the Medical Dictionary for Regulatory Activities (MedDRA) and by severity using the Common Terminology Criteria for Adverse Events dictionary.

In general, all AE tables will be presented by treatment group, causality and severity. The following will be summarized and presented overall and by treatment group:

- The number and percentage of subjects experiencing an SAE
- The number and percentage of subjects experiencing an SAE by preferred term and by severity of event
- The number and percentage of subjects experiencing an SAE by preferred term and by relationship to study drug
- The number and percentage of subjects experiencing an AE
- The number and percentage of subjects experiencing an AE by preferred term and by severity of event
- The number and percentage of subjects experiencing an AE by preferred term and by relationship to study drug
- The number and percentage of AEs that cause a subject to discontinue study drug
- The number and percentage of AEs leading to death.

Adverse events will be coded using the Medical Dictionary for Regulatory Activities (MedDRA) central coding dictionary. Adverse events will be described in summary tables and in individual listings for the DSMB reports.

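### Two listed adverse events can only occur at Month 3 or later, but their percentages are taken over everyone who received one dose

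*Protocol*

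**What the plan says.** Safety is the primary objective in both documents. Protocol 12.6 and SAP 11.1 base the primary safety analysis on everyone randomized and dosed at least once ("based on the as-treated population, defined as subjects who are randomized and receive at least one dose of study agent"). SAP section 7 words the Safety Population slightly differently, as patients who had PRK and "who receive treatment with at least one drop of study agent during the post-treatment follow-up". The planned summaries are counts and percentages of subjects, such as "The number and percentage of subjects experiencing an AE", with breakdowns such as "The number and percentage of subjects experiencing an AE by preferred term and by severity of event". SAP 11.1 compares the arms with chi-squared or exact mid-p methods.

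Protocol 5.4 collects ocular adverse events from randomization to Month 12. Two of the nine events listed in Protocol 6.1.2 are late by definition: "Poor refractive outcome (worse than 20/40 at 3 months or beyond" and "Pain or severe irritation at 3 months or beyond".

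Both documents expect some loss. Protocol 12.5 sets enrolment at 63 against 56 completers, partly to "allow for a small number of patients being lost to follow-up"; SAP section 6 gives the same reasons but enrols 60. SAP 8.2 leaves withdrawals to outcome-specific strategies. It adds that, if losses are substantial, baseline characteristics and "available information on components of efficacy outcomes will be reviewed and compared to subjects not withdrawn". SAP section 11 contains no strategy for incomplete safety follow-up.

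**The concern.** A percentage of everyone dosed treats each patient without a recorded event as a patient without the event. For events that can arise in the first weeks this is a usual convention and does little harm. For the two late events it does not fit the definition: someone who leaves at Month 1 could not have met either one, yet lowers both percentages.

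The same can happen to patients who stay in the study. The Month 1 to Month 12 columns of the Schedule of Events carry the footnote allowing telehealth or phone contact, so a retained patient may have no chart acuity at Month 3 or later.

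The plan deals with this problem for healing time, a secondary objective. SAP 10.1 treats unhealed eyes of early dropouts as missing, and SAP 10.1.1 adds a clustered log-rank test with censoring. Safety, the primary objective, has no counterpart. At stake are late-event percentages that look somewhat better than the data support and, if one arm loses more patients, a comparison tilted towards that arm.

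**Working it through.** **Inputs from the documents.** Enrolled N = 63 (Protocol 12.5) or 60 (SAP section 6); completers 56 in both. The margin is 63 − 56 = 7, or 7/63 = 11.1%, and 60 − 56 = 4, or 4/60 = 6.7%. The safety sections state no event rate, sample size or power, so there is no safety figure to reproduce. The detectable-difference table concerns healing time and is unaffected.

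**Assumptions.** The documents give no risk for the late events; 5%, 10% and 20% are used for illustration. All L losses are placed before Month 3, and the risk p is the same in lost and retained patients.

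**Step 1, overall percentage.** Only N − L patients can show a late event, so the expected percentage over everyone dosed is p × (N − L)/N. The factor is 56/63 = 0.889 (Protocol) or 56/60 = 0.933 (SAP).

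| Assumed risk | Shown, 7 of 63 lost | Shown, 4 of 60 lost | Shown, assessed only |
|---|---|---|---|
| 5% | 4.4% | 4.7% | 5% |
| 10% | 8.9% | 9.3% | 10% |
| 20% | 17.8% | 18.7% | 20% |

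**Step 2, comparison of arms.** Take 63 as 32 and 31, with the same true risk in both arms.

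| Losses (arm of 32, arm of 31) | Risk 10% | Risk 20% |
|---|---|---|
| 3, 4 | 9.1% v 8.7% | 18.1% v 17.4% |
| 5, 2 | 8.4% v 9.4% | 16.9% v 18.7% |
| 7, 0 | 7.8% v 10.0% | 15.6% v 20.0% |

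The last row is the extreme: 10% × 25/32 = 7.8%. If each loss is equally likely to fall in either arm, all seven fall in the same arm with probability 2 × (1/2)^7 = 2/128 = 1.6%. With 4 of 60 lost, all from one arm of 30, a 10% risk shows as 10% × 26/30 = 8.7% v 10.0%. When both arms lose the same proportion, their ratio does not change.

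For scale, the standard error of the difference at 10% risk is √(0.10 × 0.90 × (1/32 + 1/31)) = 7.6 percentage points. The artefact in the extreme row is 2.2 points.

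**Step 3, precision when no event is seen.** The one-sided 95% upper limit is 1 − 0.05^(1/n). It is 8.9% on 32 dosed and 11.3% on 25 assessed, so the larger denominator also overstates how much has been ruled out.

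**Step 4, what the assessed denominator cannot repair.** With p = 10% among 56 assessed, 5.6 events are expected. Counting every unassessed patient as an event gives (5.6 + 7)/63 = 20.0%, or (5.6 + 4)/60 = 16.0%. These are bounds. The assessed-only figure stays at 10%, because it assumes that loss is unrelated to the outcome.

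**The case against.** Everyone randomized and dosed is a usual safety population, and nothing is wrong with it in itself. Several further points stand.

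- A reader might infer that a patient lost early is counted as free of every adverse event. The documents do not support that: events recorded before the loss remain in the tables, and SAP 8.2 uses all available data. Seven of the nine listed events are not confined to Month 3 or later.
- A reader might infer that losses would go unseen. SAP 9.1 reports withdrawals and SAP section 7 promises a CONSORT flow, although neither commits to the number assessed at Month 3 or later.
- Late vision is also examined elsewhere. SAP 10.3.1 compares acuity between arms at the later visits, and SAP 11.2 reports loss of best corrected vision at 6 months and 1 year. An excess of poor late vision in one arm would not rest on the adverse event table alone. SAP 11.2, however, does not say who is in its denominators.
- Seven losses is not the plan's forecast. The margin also serves to add safety data, and the documents do not say when losses would occur.

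These points limit the size of the problem. They do not supply an assessed denominator or a missing-data rule for the two late events.

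**Conclusion.** The concern holds for the two events defined at 3 months or beyond, and it is minor. Followed as written, the plan understates their percentages by the fraction of patients not assessed from Month 3 on: at most about 11% relative on the Protocol's enrolment margin and 7% on the SAP's, or roughly one percentage point on a 10% risk. Those sizes assume that the whole margin is lost before Month 3 and that risk is equal in lost and retained patients. Missed late assessments among retained patients would add to them.

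A reader might go further and infer a substantial bias in favour of pAF. The documents give no reason to expect more loss in that arm, and even the extreme split produces a gap well below one standard error. Heavy loss among patients who had the event could do more harm, but that is speculation. A change of denominator would not cure it, which is why a bound is needed as well.

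**What to change.** In Protocol 12.6 and SAP 11.1, for the two late events:

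1. Use as the main denominator the patients assessed for that event at least once at Month 3 or later. Set it separately for each event, since a phone contact may establish pain but not chart acuity.
2. Show the number not assessed, by arm, and keep the all-dosed percentage alongside.
3. State that the assessed-only percentage assumes loss is unrelated to the outcome, and add a simple bound counting unassessed patients as events.

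Apply the same assessed denominator to the 6-month and 1-year vision-loss proportions in SAP 11.2. A single cumulative-incidence estimate for any ocular adverse event, censored at last assessment, is optional; curves for each preferred term are not needed with about 60 patients. While editing, reconcile the enrolment figures (63 and 60) and the safety-population wordings (one dose, one drop, and one study day in SAP 3.2.4).

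The cost is a few sentences and a little more programming, with no new data collection. The late-event percentages will rest on smaller denominators and look slightly less favourable.

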13.1 Clinical Site Data Management

The Data Coordinating Center (DCC) will develop an electronic data capture system for this trial. Currently the DCC uses multiple applications, such as OpenClinica or REDCap, and will elect to use the most appropriate application at the time of implementation of the study.

The DCC will use an electronic discrepancy management system to notify sites of inconsistent or erroneous data entry, which will be corrected by the clinical site. The discrepancy/management system maintains an audit trail of all discrepancy resolution.

13.2 Study Monitoring

The investigators recognize the importance of ensuring data of excellent quality. Study monitoring is critical to this process. Monitoring has been a very effective tool for maintaining data quality in previous network studies, and we will utilize this process to ensure excellent quality data in the proposed study. The DCC utilizes risk-based methodology to identify and correct problems that may arise at sites. The risk-based approach to monitoring focuses on oversight activities and preventing or mitigating key risks to data quality, as well as to processes critical to human subject protection and integrity of the trial or study.

Study monitors must be provided with appropriate access to study materials and the medical records for study subjects. If the medical records are in electronic form, the clinical investigator or an authorized individual must provide any assistance necessary to facilitate the study monitor's review of data in the electronic medical record.

13.2.1 Site Monitoring Plan

A supplemental study-specific risk-based monitoring plan, separate from the protocol will be completed which outlines specific criteria for monitoring. This plan may include the number of planned site visits, criteria for focused visits, additional visits or remote monitoring, a plan for chart review and a follow up plan for non-compliance. The monitoring plan also describes the type of monitoring that will take place (e.g., sample of all subjects within a site; key data or all data), the schedule of visits, how they are reported and a time frame to resolve any issues found.

13.2.2 Clinical Site Monitoring

Site monitoring visits will be performed by a trained site monitor during the study period to ensure regulatory compliance, patient safety, and to monitor the quality of data collected. Essential document binders, regulatory documents and data collection forms may be reviewed. Interim visits will take place depending on grant budget, site enrollment, and compliance issues identified. The site monitor will provide each site with a written report, and sites will be required to follow up on any deficiencies. It is anticipated that the study monitoring visits for this protocol will consist of a site initiation visit (prior to patient enrollment), interim visits, and a close out visit. The site initiation may take place as group training made up of site investigators and research assistants.

13.2.3 Remote Monitoring

The Data Coordinating Center may supplement on-site monitoring with remote monitoring activities. Remote monitoring involves detailed review of the data entered by the site and consultations with the site investigator and/or research coordinator to review safety and data quality. This may require uploading copies of medical records, patient study files, regulatory documentation, or other source documents for the monitor to review. Alternatively, other methods, such as remotely viewing source documentation, may be utilized. This helps assure protocol compliance and accurate data collection. The Data Coordinating Center may conduct more remote monitoring activities early in the trial to assure protocol compliance and identify any training issues that may exist. Remote monitoring documents will be retained in accordance with federal requirements.

14 Protection of Human Subjects

14.1 Institutional Review Board Approval

The Data Coordinating Center and clinical center PI must obtain approval from the IRB prior to participating in the study. The Data Coordinating Center will track IRB approval status and will not permit subject enrollment without documentation of initial IRB approval and maintenance of that approval throughout subsequent years of the project.

14.2 Informed Consent

If a subject is greater than 18 years of age or attains the age of 18 years during the study period, informed consent is required. Subjects who are capable of giving consent and who are alert and competent, will be asked, following an appropriate discussion of risks and benefits, to give consent to the study.

14.3 Potential Risks

Loss of confidentiality of the subject is a potential risk of the study; however, safeguards are in place to protect against this. There are no known or anticipated additional medical risks from participating in the trial.

14.4 Protection Against Potential Risks

Regarding loss/breach of privacy and confidentiality, all applicable parties (e.g. clinical sites, DCC) will be responsible for ensuring that appropriate data security procedures are in place.

14.5 Potential Benefits

There may be a potential benefit in helping decrease pain and healing time with pAF treatment.

15 Regulatory Considerations

15.1 Food and Drug Administration

This trial is being conducted under an Investigational New Drug application. The clinical investigator at each participating site will complete a Form FDA 1572, "Statement of Investigator."

An annual progress report will be submitted to the FDA within 60 days of the anniversary of the date that the IND went into effect (21 CFR 312.33).

15.2 Health Insurance Portability and Accountability Act

Data elements collected include the date of birth and date of admission. Prior to statistical analyses, dates will be used to calculate patient age at the time of the study events. The final data sets (used for study analyses and archived at the end of the study) will be de-identified, and will exclude these specific dates. Data elements for race, ethnicity, and gender are also being collected. These demographic data are required for Federal reporting purposes to delineate subject accrual by race, ethnicity, and gender.

15.3 Inclusion of Women and Minorities

There will be no exclusion of patients based on gender, race, or ethnicity.

15.4 Protocol Amendments

Any amendments or administrative changes to an IRB approved protocol will not be initiated without submission of an amendment for IRB review and approval. Any amendments to the protocol that significantly affect the safety of subjects, the scope of the investigation, or the scientific quality of the study are required to submit the amendment for FDA review.

16 Data Coordinating Center

The Data Coordinating Center (DCC) in the Department of Pediatrics at the University of Utah School of Medicine provides data coordination and management services for a variety of national research networks. Anchoring these services is a new state-of-the art, energy efficient data center completed in 2013. The data center facility supports more than 1400 users around the world and provides a secure, reliable, enterprise-wide infrastructure for delivering critical DCC systems and services. The new data center was built using high industry standards and energy efficient cooling solutions. The data center is cooled by Rittals LCP inline cooling technology, providing efficiency, redundancy and modularity. Cooling is based upon a hot/cold aisle design that allows for even air distribution with minimal hot spots. The data center electrical power system contains a redundant Mitsubishi uninterruptible power system (UPS) with a diesel backup generator. The data center is protected with a FM200 fire suppression system, early warning smoke detectors and a heat detection warning system to act as a secondary system to the smoke detectors. Security guards are on-site conducting access control and rounds. Entry

into the data center is restricted by card access and layered security measures and controls. The data center and external building access points are monitored with video surveillance.

- In 2011 the data center began a large scale VMware server virtualization deployment. Currently, the data center has virtualized about 99% of its environment. The virtual environment consists of more than 200 virtual servers. The data centers virtualization solution provides key advantages: high availability in the event of hardware failure, virtual servers automatically go back online in a seamless process.
- Flexible infrastructure disk storage, memory and processor capacity can be increased or reallocated at any time.
- Rapid deployment servers can be provisioned on-demand with minimal waiting on hardware or software.

The data center also enhanced its storage resources by implementing a networked storage system to support its virtualized environment. The data center currently manages over 50 terabytes of data. The storage solution consists of Dells EqualLogic PS Series Storage system for providing a virtualized storage area network (SAN). Some of the benefits that are realized through this technology are:

- Storage architecture is no longer be a bottleneck for IT services;
- Performance is better than with the previous architecture;
- Tiered storage is now possible;
- Provisioning and reclamation of SAN disk will be much easier; and most important;
- The new architecture includes a redesign of the SAN fabric to include complete redundancy.

Production servers running critical applications are clustered and configured for failover events. Servers are backed up with encryption through a dedicated backup server that connects across an internal 10 gigabit network to a tape drive. DCC storage area networking (SAN) applications, clusters, and switch-to-switch links are also on a 10 gigabit network. Incremental backups occur hourly Monday through Friday from 6 am to 6 pm. Incremental backups also are performed each night with full system backups occurring every Friday. Tapes are stored in a fireproof safe inside the data center facility, and full backups are taken off site on a weekly basis to an off-site commercial storage facility. In the event of catastrophic failure, such as a fire in

the server facility, daily backups would probably survive because of the fire suppression system and fireproof safe, but there would be obvious delay in re-establishing data center function because the servers will not survive such a disaster. Total destruction of the data center facility could cause the loss of up to one weeks data. In future investments, the data center is making co-location, disaster recovery and business continuity solutions a top priority. DCC information systems are available 24 hours a day, 7 days a week to all users unless a scheduled maintenance interruption is required. If this occurs, we notify all users of the relevant systems, and data entry can be deferred until after the interruption is over. Critical systems availability has exceeded 99.9% for the past two years, and there has been no unscheduled downtime in over five years.

